10.1 Disposition of Participants and Discontinuations

This following will be presented in a summary table:

- Total number of participants screened (i.e., participants who gave informed consent)
- Number of screened participants who discontinued from the trial prior to treatment overall and grouped by the main reason for discontinuation:
 - Participant did not meet all eligibility criteria
 - Withdrew consent
 - Other (COVID-19-related and COVID-19-non-related)
- Number of randomized participants
- Number of randomized participants who did not receive treatment (as applicable)
- Number of treated participants by treatment T1, T2, R1, R2 and overall
- Number and percentage of treated participants who completed study by treatment T1, T2, R1, R2 and overall
- Number and percentage of treated participants who discontinued the study overall and number of subjects who discontinued treatment by treatment T1, T2, R1, R2, with the primary reason of discontinuation: :
 - Adverse event
 - Lost to follow-up
 - Protocol non-compliance
 - Death
 - Withdrew consent

- Other (COVID-19-related and COVID-19-non-related)

A listing of discontinued participants will be provided.

A listing of participants affected by the COVID-19 related study disruption by unique subject number identifier will also be provided.

10.2 Protocol Deviations

10.2.1 Important Protocol Deviations

Listings of important protocol deviations will be provided including the date and relative day in relation to dosing in the relevant period.

10.2.2 Reasons Leading to the Exclusion from an Analysis Set

All criteria/reasons leading to the exclusion of a participant from an analysis set will be listed based on the safety set.

Reasons for excluding individual PK concentrations will also be listed separately and flagged in the main listing based on the Safety Analysis Set.

11 Demographics and Other Baseline Characteristics

11.1 Demographics

Summaries will be given for both the safety and the PK set, if different.

Demographic characteristics will be listed by participant and treatment sequence and summarized by treatment sequence and overall using the following information from the Screening/Baseline Visit eCRF pages.

Demographic characteristics:

- Sex: male, female, undifferentiated
- Race: American Indian or Alaska Native, Asian, Black or African American, Native Hawaiian or Pacific Islander, White, Other
- Ethnic origin - Hispanic or Latino: yes, no
- Ethnic origin - Japanese: yes, no
- Age (years): summary statistics
- Height (cm) at Screening : summary statistics

- Weight (kg) at Screening : summary statistics
- BMI (kg/m²) at Screening: summary statistics

Age will be taken from the eCRF and cannot be derived from the data because only the year of birth is collected in the eCRF.

BMI will be re-derived (ie, not taken directly from the database) according to the following formula:

- $BMI (kg/m^2) = \text{weight (kg)} / (\text{height (m)} * \text{height (m)})$

11.2 Medical History

The medical history will be listed by participant including the preferred term (PT) and MedDRA system organ class (SOC) body using MedDRA, current version.

11.3 Other Baseline Characteristics

Other baseline characteristics will be listed by participant and summarized by treatment sequence and overall using the following information from the Screening/Baseline Visit eCRF pages.

Other baseline characteristics may include:

- Smoking status
- Alcohol consumption

12 Previous or Concomitant Medications/Procedures

Previous medications are medications, other than trial medications and pre-medications for trial drug, which started and stopped before first administration of trial drug.

Concomitant treatments are medications, other than trial medications, which are taken by participants any time on-trial (on or after the first day of trial drug treatment for each participant).

In case the date values will not allow to unequivocally allocate a medication to previous or concomitant medication the medication will be considered as concomitant medication.

Any previous and concomitant medication will be encoded with WHO-DD, latest version. Prior and concomitant medications will be listed by participant (safety set).

The following information will be displayed in a listing: generic or trade name (as reported in CRF), WHO drug name, dose/unit, route, frequency, reason for use, start/end date and time.

Concomitant procedures will be presented in a data listing.

13 Treatment Compliance and Exposure

The dosing of each participant is monitored by the study nurse or investigator. A listing of date and time of each drug administration and each blood sampling, including time deviations as well as measured rac-PZQ, R-(-)-PZQ and S-(+)-PZQ concentration, will be provided sorted by participant.

14 Efficacy Analyses

Not applicable.

15 Safety Analyses

The subsections in this section include specifications for summarizing safety endpoints that are common across clinical trials such as adverse events, laboratory tests and vital signs.

Safety data analysis will be conducted on the Safety Analysis Set.

15.1 Adverse Events

Adverse Events will be listed by treatment T1, T2, R1, R2.

Generally, the number and percentage of participants experiencing at least one TEAE will be summarized by treatment T1, T2, R1, R2, by total T, total R and overall as well as the number of events.

A TEAE is an AE with onset after start of treatment or with onset date before the treatment start date but worsening after the treatment start date. Tables by relationship to trial drug and by severity will be generated. AEs will be coded using Medical Dictionary for Regulatory Activities (MedDRA) terminology, latest version.

If an event was reported more than once, the worst severity will be tabulated.

Incomplete TEAE-related dates will be handled as follows:

- In case the onset date is missing completely or missing partially but the onset month and year, or the onset year are equal to the start of trial treatment then the onset date will be replaced by the minimum of start of trial treatment and TEAE resolution date.
- In all other cases the missing onset day or missing onset month will be replaced by 1.
- Incomplete stop dates will be replaced by the last day of the month (if day is missing only), if not resulting in a date later than the date of the participant's death. In the latter case, the date of death will be used to impute the incomplete stop date.
- In all other cases the incomplete stop date will not be imputed.

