### 1.3 Schedule of Activities

Activity/Assessment	Screening (Baseline)	Treatment Period 1, 2, 3 and 4				End of Treatment / Safety Follow-up	Comments	
		Day -28 to -1	Day -1/7/14/21	Day 1/8/15/22 a				Day 2/9/16/23
Study Day							a Assuming 7 days for washout between the 4 treatment periods.	
Period Day		-1	1		2			
Study Day timepoints			-1 h	-0.5 h	0 h	24 h		
ICF signature available	X							
Demographics (incl. BW and BMI), medical history and history of medication	X							
Smoking history, alcohol intake, use of caffeine or xanthine-containing beverages	X							
Serology test	X							
Physical examination b	X	X				X	b According to the CRO procedure.	
Vital signs c (BP, HR, body temperature)	X	X	X			X	X	c At visits where assessment time points coincide with each other, the following procedure should be followed: perform vital signs and ECG assessments within 15 min before the specific time point and PK blood sampling on time.
12-Lead-ECG c	X		X			X	X	c At visits where assessment time points coincide with each other, the following procedure should be followed: perform vital signs and ECG assessments within 15 min before the specific time point and PK blood sampling on time.
Safety lab tests	X	X				X	X	
Drug screening urine	X	X						

Activity/Assessment	Screening (Baseline)	Treatment Period 1, 2, 3 and 4				End of Treatment / Safety Follow-up	Comments
Study Day	Day -28 to -1	Day -1/7/14/21	Day 1/8/15/22 a			Day 2/9/16/23	Day 27 (± 3 days)
Period Day		-1	1			2	
Study Day timepoints			-1 h	-0.5 h	0 h	24 h	
Alcohol breath test	X	X					
Confinement d		[-----X-----]					d Confinement from the morning of Day -1/7/14/21 (about 20-24 hours prior to each IMP administration) until the morning of Day 2/9/16/23.
Standardized breakfast				X			
In/exclusion criteria check/recheck	X	X	X				
Randomization			X f				f Randomization will be performed in eligible participants on Day 1 only.
Administration of IMP					X		

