#### 4.2.3 Washout Period

The minimum washout period between each investigational medicinal product (IMP) administration is set to 7 days in accordance with the WHO Guidance. It is expected that for logistic reasons a washout period of 7 days is convenient. From a scientific point of view a shorter

period could be envisaged as the mean half-life of rac-PZQ is 2.5 hours while the half-life of the main trans-OH-rac-PZQ metabolite is approximately 4.5 hours (Geomean; min-max 2.8 to 6.3 hours; data on file). In addition, for individual cases a longer washout period could be allowed.

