### 8.3.1 Time Period and Frequency for Collecting Adverse Event and Serious Adverse Event Information

The AE reporting period for safety surveillance begins when the participant is initially included in the study (date of first signature of informed consent/date of first signature of first informed consent) and continues until the end of the Safety Follow-up.

Any SAE assessed as related to study intervention must be recorded and reported, as indicated in [Appendix 4](#), whenever it occurs, irrespective of the time elapsed since the last administration of study intervention.

The method of recording, evaluating, and assessing causality of AEs (including SAEs) and the procedures for completing and transmitting SAE reports are in [Appendix 4](#).

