### 9.4 Statistical Analyses

Statistical analysis will be performed using the computer program package SAS® System (release 9.2 or later version; SAS Institute, Cary NC, USA). Details on the statistical analysis will be presented in the integrated analysis plan prior to database lock.

The statistical analysis will not be started until all data have been corrected and checked for plausibility, and until all necessary coding and assessments have been completed.

Medical history and AE terms will be coded with the latest version of the Medical Dictionary for Regulatory Activities (MedDRA; version 22.0 or later); concomitant medication will be coded with WHO Drug Dictionary, WHO Drug Reference List and Anatomical Therapeutic Chemical Classification System, latest version. Versions of dictionaries used for coding will be defined in the Data Management Plan (DMP).

All data recorded during the study will be presented in individual data listings.

All data will be evaluated as observed, no imputation method for missing values will be used except for missing dates/times in AE data which will be performed for the classification of treatment-emergence, assigning AEs to treatment periods and for calculation of duration. The handling of concentration values below the limit of quantification will be described in the statistical analysis plan.

Summary statistics will be provided for all endpoints.

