## Recording and Follow-Up of AE and/or SAE

It is important that each AE report include a description of the event, its duration (onset and resolution dates and also onset and resolution times, when it is important to assess the time of AE onset relative to the recorded study intervention administration time), its severity, its causal relationship with the study intervention, any other potential causal factors, any treatment given or other action taken, including dose modification or discontinuation of the study intervention, and its outcome. In addition, serious cases should be identified, and the appropriate seriousness criteria documented.

Specific guidance is in the CRF Completion and Monitoring Conventions provided by the Sponsor.

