15.1.1 All Adverse Events

All AEs recorded during the course of the trial (i.e. assessed from signature of informed consent until the end of treatment/safety follow-up visit) will be coded according to MedDRA latest version and assigned to a SOC and PT.

TEAEs will be summarized by worst severity, using MedDRA latest version PT as event category and MedDRA primary SOC body term as Body System category. The severity of AEs will be assessed by the investigator per the Qualitative Toxicity Scale as detailed in the study protocol: mild, moderate, severe.

TEAEs related to trial treatment are those events with relationship related, or missing, or unknown.

The following will be summarized in an overview table with the number and percentage of participants (and the number of events) by treatment and overall:

- Any TEAEs
- Any trial treatment-related TEAEs
- Any serious TEAEs
- Any trial treatment-related serious TEAEs
- Any severe TEAE
- Any trial treatment-related severe TEAEs
- Any TEAEs leading to death
- Any trial treatment-related TEAEs leading to death

TEAEs will be summarized by treatment and total T, total R and overall in tables with:

- The number and percentage of participants by treatment with at least one TEAE and the number of events overall and by SOC and PT. SOC terms will be sorted alphabetically and PTs within each SOC term will be sorted by descending overall frequency.
- The number and percentage of participants by treatment with at least one non-serious TEAE and the number of non-serious TEAE applying frequency threshold of 5% according to SOC (i.e. SOC events with frequency > 5% in any arm). SOC terms will be sorted alphabetically and PTs within each SOC term will be sorted by descending overall frequency.

In addition the following tables will be provided. SOC terms will be sorted alphabetically and PTs within each SOC term will be sorted by descending frequency (based on all treatment groups combined):

- A table by severity of TEAEs with the number and percentage of participants by treatment with at least one TEAE and the number of events by SOC and PT.
- A table by relationship to trial treatment with the number and percentage of participants by treatment with at least one TEAE and the number of events by SOC and PT.

Pre-treatment AEs (AEs with onset after informed consent but before start of treatment) and TEAEs will be listed separately.

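### The worsening leg of the SAP 15.1 TEAE definition compares calendar dates, so an AE present before the first dose that worsens later on the dosing day is not counted as treatment-emergent

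*SAP*

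**What the plan says.** SAP 15.1 has two legs. The first covers new events: "A TEAE is an AE with onset after start of treatment". The second covers events already present, namely those with "onset date before the treatment start date but worsening after the treatment start date". Under SAP 15.1.1, "Pre-treatment AEs (AEs with onset after informed consent but before start of treatment) and TEAEs will be listed separately". The imputation rules in SAP 15.1 deal with incomplete dates only.

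Other parts of the plan work with clock times. Protocol 9.4 makes an exception to its no-imputation rule for "missing dates/times in AE data which will be performed for the classification of treatment-emergence". Protocol Appendix 4, on recording AEs, asks for "onset and resolution dates and also onset and resolution times, when it is important to assess the time of AE onset relative" to dosing. SAP section 9 derives time from dosing to a TEAE in days, hours and minutes. SAP section 7 declares no change from the protocol's planned analyses.

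AEs are collected well before dosing. Protocol 8.3.1 states that "The AE reporting period for safety surveillance begins when the participant is initially included in the study", which it dates from signature of consent.

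**The concern.** The purpose of the second leg is to catch an existing complaint that gets worse under drug. Because it compares dates, it cannot recognise worsening on the day of dosing, and it cannot admit any event whose onset falls on that day before the dose. Such events go to the pre-treatment listing and drop out of the TEAE overview and the tables by severity, relationship, SOC and PT.

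Occurrence of TEAEs is a secondary endpoint. The case is realistic. Participants are confined from Day -1, fast for at least 10 hours and go without caffeine for 48 hours, so a mild headache before the dose is plausible. Protocol 2.3 lists headache as very common with the reference product. A mild headache that becomes moderate an hour or two after the tablets is what the second leg exists to catch.

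**Working it through.** **Step 1. Apply the rule as written.** Leg 1: onset later than the start of treatment. Leg 2: onset date earlier than the treatment start date, and worsening date later than the treatment start date. The alternative is a date/time rule: onset at or after the first dose, or onset before it with worsening at or after it. Five test cases, with the first dose on the morning of Day 1:

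| Case | Leg 1 | Leg 2 | SAP as written | Date/time rule |
|---|---|---|---|---|
| a. Onset Day -1, worse 3 h after dose | no | no: worsens on the start date | not a TEAE | TEAE |
| b. Onset Day -1, worse on Day 2 | no | yes | TEAE | TEAE |
| c. Onset Day 1 before dose, worse 3 h after dose | no | no: onset date equals start date | not a TEAE | TEAE |
| d. Onset Day 1 before dose, worse on Day 2 | no | no: onset date equals start date | not a TEAE | TEAE |
| e. New onset 1 h after dose | yes | not needed | TEAE | TEAE |

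The written rule captures 2 of 5 and the date/time rule 5 of 5. Case d shows that for Day 1 pre-dose onsets the gap does not close at midnight.

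**Step 2. How much of the exposure falls in the excluded window?** The documents give no clock time for dosing. The Schedule of Activities has confinement starting "about 20-24 hours prior to each IMP administration) until the morning of Day 2/9/16/23", and the 24-hour time point falls on that second day, so dosing is in the morning. I assume 07:00 to 11:00, which puts midnight 17 to 13 hours after the dose. Protocol 4.2.3 says that "the mean half-life of rac-PZQ is 2.5 hours" and gives about 4.5 hours for the main metabolite.

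Fraction remaining at midnight = 0.5^(hours to midnight / half-life), ignoring absorption and formation time:

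| Assumed dose time | Hours to midnight | rac-PZQ, 2.5 h | Metabolite, 4.5 h |
|---|---|---|---|
| 07:00 | 17 | 0.5^6.8 = 0.9% | 0.5^3.78 = 7.3% |
| 09:00 | 15 | 0.5^6.0 = 1.6% | 0.5^3.33 = 9.9% |
| 11:00 | 13 | 0.5^5.2 = 2.7% | 0.5^2.89 = 13.5% |

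On these assumptions, about 97% to 99% of parent drug and 86% to 93% of metabolite is eliminated before the first date on which leg 2 can accept a worsening.

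**Step 3. Does any other text repair it?** No. SAP 15.1 imputes missing onset dates but has no rule for a missing time on the dosing day, although Protocol 9.4 refers to times for this purpose. Its imputation can also set a missing onset equal to the start of treatment. Read strictly, that is neither after the start nor on an earlier date, so the boundary itself is not fully specified.

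**The case against.** The strongest defence is that this is loose drafting in one clause. Protocol 9.4 and SAP section 9 point to clock times, and SAP 15.1.1 defines pre-treatment events by the start of treatment, so a programmer might apply a date/time rule anyway. That is possible, but the clause gives an explicit rule in dates, and nothing in the SAP overrides it.

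The second defence is about records. If the CRF opens a new record with its own onset time when severity changes, leg 1 would capture the worsening. The SAP merges several records of one AE only for duration and takes the worst severity only for tabulation. It does not say which onset decides treatment-emergence. This stands as a real uncertainty: the CRF is not among the documents, and Appendix 4 lists onset and resolution times but no time of worsening. The same gap limits any date/time rule, so the fix has to address it.

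Several stronger readings are tempting and not supported:

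- A reader might infer that dosing-day AEs in general are missed. They are not; leg 1 counts every new post-dose onset.
- A reader might infer that all AE tables are affected. The SAE table in SAP 15.2.2 is not restricted to TEAEs, and the AE listings keep the events.
- A reader might infer a percentage of TEAEs lost. That needs the share of participants with an ongoing AE at dosing and the share who worsen, and the documents give neither. Participants must be overtly healthy, and eligibility is rechecked on Day -1 and one hour before dosing. The earlier study with 24 TEAEs used other formulations at 40 and 60 mg/kg, against 12.6 to 21.8 mg/kg here.
- A reader might infer from the 2.5-hour half-life that the rule drops the events most likely to be caused by the drug. The metabolite lasts longer, and the documents do not show that AE timing follows plasma level.

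**Conclusion.** The point holds as a misclassification rule in SAP 15.1. As written, a pre-existing AE that worsens after dosing on the dosing day is not a TEAE, and an AE that begins on Day 1 before the dose can never become one. The TEAE summary tables would undercount. The number affected is probably small and may be zero.

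This assumes that treatment start means the first dose of the study, so that only AEs arising between consent and the Period 1 dose are exposed. The SAP does not say so; applied per period, the rule would reach all four dosing days. It also assumes that a worsening does not open a new record with its own onset.

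Nothing suggests that one product is favoured. Under the first-dose reading, Period 1 is test in one sequence and reference in the other, randomized 1:1. AEs are summarised descriptively, and the bioequivalence conclusion does not depend on this flag. It is a worthwhile correction of low consequence.

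**What to change.** Before database lock, replace the definition in SAP 15.1 with a date/time rule along these lines:

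> An AE is treatment-emergent if its onset is at or after the date and time of first study drug administration, or if its onset is earlier and its severity increases at or after that date and time. If the time of onset or of worsening is missing and the date is the dosing date, the AE is classed as treatment-emergent. Worsening is identified from the CRF record of the severity change.

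List events that qualify by worsening with the TEAEs in SAP 15.1.1. The missing-time sentence also supplies the handling that Protocol 9.4 promises.

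The cost is a short SAP edit and a change to one derivation. Dose times and event start times are already used in SAP section 9. The date and time of worsening must be obtainable from the CRF, which should be confirmed first. The statistical downside is that a few untimed dosing-day events that really began before dosing may be counted as TEAEs. That errs towards over-counting, which is the safer direction for a safety table.

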## **6.3 Measures to Minimize Bias: Study Intervention Assignment and Blinding**

### **6.3.1 Study Intervention Assignment**

On Day 1 participants will be assigned a unique number (randomization number) in ascending numerical order at the study site. The randomization number encodes the participant's assignment to one of the 2 sequences of the study, per the randomization schedule generated prior to the study by Nuvisan GmbH PPD.

Participants will be randomized in a 1:1 ratio to 1 of 2 sequences: T1-R1-T2-R2 or R1-T1-R2-T2.

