Repeated and unscheduled measurements will be included in the listings, but not used for statistical analysis or summary tables, unless the repeated measurement was performed due to unreliable values/technical reasons, e.g., clotted samples.

In this phase 1 PK study, missing observations will be assumed to be missing completely at random (MCAR). No action will be taken to handle missing data. A participant who withdraws prior to the last planned observation in a trial period will be included in the analyses up to the time of discontinuation.

The following treatment labels will be used:

Treatment Tx: x. administration of coated Cesol tablet, 2 tablets of praziquantel 600 mg per period,

Treatment Rx: x. administration of Biltricide[®], 2 tablets of praziquantel 600 mg per period

where x=1 or x=2 defines the first and second administration of test or reference product, respectively. These labels will be used in listings and summaries by first treatment and second treatment.

Treatment Total T: coated Cesol tablet, 2 tablets of praziquantel 600 mg per period,

Treatment Total R: Biltricide[®], 2 tablets of praziquantel 600 mg per period,

whereby these treatment labels will be used in summaries by total treatment.

10 Trial Participants

The subsections in this section include specifications for reporting participant disposition and treatment/trial discontinuations. Additionally, procedures for reporting protocol deviations are provided.

Considering the study objectives, it is planned to enroll 36 participants in the study to ensure inclusion of at least 32 evaluable participants for the treatment comparisons.

The participants will be randomized to one of the two treatment sequences: T1-R1-T2-R2 or R1-T1-R2-T2, where T is Test product and R is Reference product, with a washout period of at least 1 week in between.

	Period 1		Period 2		Period 3		Period 4
Sequence 1 (18 participants)	Test 1	Washout at least 7 days	Reference 1	Washout at least 7 days	Test 2	Washout at least 7 days	Reference 2
Sequence 2 (18 participants)	Reference 1		Test 1		Reference 2		Test 2

Test = coated Cesol tablet, 2 tablets of praziquantel 600 mg;
Reference = Biltricide, 2 tablets of praziquantel 600 mg.

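### The SAP's onset-date rule knows only one treatment start, so in this four-period crossover it places incompletely dated AEs in the wrong treatment column

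*SAP*

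**What the plan says.** SAP 15.1 gives the only rule for incomplete onset dates. Its first branch covers a date that is completely missing, or "missing partially but the onset month and year, or the onset year are equal to the start of trial treatment". In that branch "the onset date will be replaced by the minimum of start of trial treatment and TEAE resolution date". The second branch reads: "In all other cases the missing onset day or missing onset month will be replaced by 1".

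Protocol 9.4 names the purposes of imputing AE dates. Besides classifying treatment-emergence, they are "assigning AEs to treatment periods and for calculation of duration". The imputed onset therefore decides the column in which an event is counted.

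SAP 15.1 states that TEAEs are "summarized by treatment T1, T2, R1, R2, by total T, total R and overall". On the design, SAP section 10 says: "The participants will be randomized to one of the two treatment sequences: T1-R1-T2-R2 or R1-T1-R2-T2". The product thus alternates at every period.

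SAP section 7 declares no change from the protocol's planned analyses. The SAP offers no other way to allocate an incompletely dated AE to a period.

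**The concern.** The rule suits a trial with one treatment start, where the only question is whether an event came before or after it. Here the imputed date must also choose among four doses, and the rule consults only the first of them or the first of a calendar month. An event that belongs to period 2, 3 or 4 can then be credited to an earlier administration. If it moves back by one or three periods, it is credited to the other product.

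At stake is the secondary objective on safety and tolerability of test versus reference, which is read from these columns.

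The SAP does not define the start of trial treatment. The plain reading is the first dose in the trial, because the derivations in SAP section 9 add the qualifier *in period* when they mean the period's own dose. If the period dose was intended, the rule still does not say how to find the period when the date is missing.

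**Working it through.** The documents give no figure for this point, so the rule is applied as written.

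**Inputs from the documents**
- Doses on Days 1, 8, 15 and 22 (Protocol 1.3: "Assuming 7 days for washout between the 4 treatment periods").
- Sequences TRTR and RTRT; "Participants will be randomized in a 1:1 ratio to 1 of 2 sequences" (Protocol 6.3.1).
- The two branches of SAP 15.1.

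**Assumptions**
- AEs are equally frequent in each period.
- Onset is equally likely on each of days 0 to 6 after a dose.
- The AE resolves on or after the first dose.
- The AE is credited to the last dose on or before the imputed date.
- Results are averaged over every start date in a four-year span (1,461 dates).

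**Step 1: onset completely missing.** The imputed onset is always the first dose, so 100% go to period 1.
- Right administration: 1 of 4 periods = 25%; wrong: 75%.
- Right product: periods 1 and 3 share a product, so 2 of 4 = 50%; wrong: 50%.

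**Step 2: day missing, month known.** If the onset month is that of the first dose, onset becomes the first dose. Otherwise it becomes the 1st of the onset month. Two examples with onset on the dosing day:
- First dose 5 July (then 12, 19 and 26 July): AEs from all four periods go to period 1.
- First dose 20 July (then 27 July, 3 and 10 August): AEs from periods 1 and 2 go to 20 July, which is period 1. AEs from periods 3 and 4 go to 1 August, where the last dose was 27 July, which is period 2.

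Averaged over all start dates, in %:

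| True period | Credited to 1 | to 2 | to 3 | to 4 | Wrong administration | Wrong product |
|---|---|---|---|---|---|---|
| 1 | 100 | 0 | 0 | 0 | 0 | 0 |
| 2 | 86.9 | 13.1 | 0 | 0 | 86.9 | 86.9 |
| 3 | 63.9 | 23.0 | 13.1 | 0 | 86.9 | 23.0 |
| 4 | 40.9 | 23.0 | 23.0 | 13.1 | 86.9 | 63.9 |

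- Credited to period 1: (100 + 86.9 + 63.9 + 40.9)/4 = 72.9%.
- Wrong administration: (0 + 3 × 86.9)/4, about 65%.
- Wrong product: (0 + 86.9 + 23.0 + 63.9)/4, about 43%.

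**Step 3: sensitivity**

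| Case | To period 1 | Wrong administration | Wrong product |
|---|---|---|---|
| Day missing, 7-day spacing, onset days 0–6 | 72.9% | 65.1% | 43.4% |
| Day missing, 7-day spacing, onset on dosing day | 80.3% | 72.5% | 48.4% |
| Day missing, 10-day spacing, onset days 0–9 | 61.8% | 61.4% | 41.0% |
| Onset completely missing | 100% | 75% | 50% |

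**Step 4: effect on the comparison.** Take illustrative true counts of 20 AEs on T and 10 on R, split evenly over administrations and sequences, with a fraction f = 0.10 having no onset date. Each sequence carries 15 AEs, so 15 × 0.10 = 1.5 move to its period 1 product.
- T1 = 10 × 0.9 + 1.5 = 10.5; T2 = 10 × 0.9 = 9.0; total T = 19.5.
- R1 = 5 × 0.9 + 1.5 = 6.0; R2 = 5 × 0.9 = 4.5; total R = 10.5.
- The difference T − R falls from 10 to 9, that is, by the factor 1 − f.

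**The case against.** The strongest reply is that the rule will rarely be used. Participants are in the unit from the day before dosing until 24 hours after it (Protocol 4.1) and are asked about changes at every visit (Protocol 8.3.2). AE reports must carry onset and resolution dates (Protocol Appendix 4), and queries are resolved before database lock (SAP 6.2). In an earlier praziquantel trial summarised in Protocol Appendix 7, 59 of 68 TEAEs resolved within 24 hours of dosing. An AE with a known date but no clock time is not touched by this rule. This stands: the percentages apply only to incompletely dated AEs, and with complete dates the effect is nil. Participants are, however, out of the unit for most of each washout, so recalled dates can occur.

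It can also be said that safety is only summarised descriptively and that no decision rule hangs on these columns. That limits the consequence but does not make the allocation right.

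A reader might infer more than the documents support:
- *That every incomplete date moves to first dose.* A partial date in a later month goes to the 1st of that month, which can fall in any period.
- *That the product is always wrong.* A period 3 event moved to period 1 keeps its product. The 87% for period 2 is the worst period, not the average.
- *That the T2 and R2 columns are emptied.* Only incompletely dated events move.
- *That one product is favoured.* With 1:1 allocation to TRTR and RTRT the error is symmetric.
- *That the bioequivalence conclusion is at risk.* The PK analysis does not use AE dates.

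Finally, 7 days is the minimum washout and longer gaps are allowed. At 10 days the shares fall only modestly.

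**Conclusion.** The point holds, with a limited practical effect. As written, SAP 15.1 cannot do what Protocol 9.4 asks of it, which is to assign an incompletely dated AE to its treatment period. This is a wrong rule for the design, not merely missing detail, because a programmer who follows it will fill specific columns with events that belong elsewhere.

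The step 3 shares are conditional on an incomplete date and rest on equal events per period and the stated onset windows. The step 1 figures also need resolution on or after first dose. The documents do not say how many dates will be incomplete; the number should be small. The result is a diluted T − R difference and some events shifted from T2 and R2 to T1 and R1. The correction is worth making because it is cheap and can be settled before database lock.

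**What to change.** Amend SAP 15.1 as follows.

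1. Keep the existing rule only for deciding whether an AE is treatment-emergent.
2. For period assignment, use the latest dosing date that is compatible with the known date parts, not later than the AE resolution date, and before the visit at which the AE was first recorded. Impute the onset to that date. Define compatible as no later than the last onset date that the known parts allow. If that dose falls in a month before the known onset month, assign the AE to that dose but keep the first of the known month as the onset date.
3. Define the visit limit as the last dose given before that visit, not as the visit's period label. The Schedule of Activities counts Days 7, 14 and 21 as the day before dosing in the next period. Using the label would credit an AE from the washout days to the other product.
4. If no dosing date is compatible, for example because the AE resolved before first dose, keep the current minimum rule and class the AE as pre-treatment.
5. Flag every AE with an imputed onset in the listing.
6. Define the start of trial treatment as the first dose in the study.

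If each AE is recorded before the next dose, this rule returns the true period.

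The cost is one SAP paragraph and a small programming change. There are two small downsides. Choosing the latest compatible dose gives the shortest AE duration, and the visit of first recording must be available in the CRF data, which the documents do not confirm.
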